6. SAFETY

Data Safety Monitoring Board

This committee will be composed of a group of three scientists who are not directly involved with the study and are qualified to serve in an advisory capacity in order to evaluate safety and efficacy of the trial. The safety monitoring board will convene before the study begins and, after the trial is underway, at regular intervals that they determine to be appropriate or at other times at the request of the study investigators.

Physical Examination and Clinical Laboratory Tests

A physical examination will be performed at the screening visit (unless one has been completed within the past 30 days and documented in medical records accessible to the research staff). Clinical laboratory tests including CBC, CMP, thyroid stimulating hormone (TSH), and urinalysis will also be performed. The study physician will determine the participant's medical eligibility for the study after reviewing the findings from the screening physical examination and laboratory tests.

In the event that the study physician determines that a participant's lab value is clinically significant, the participant will be made aware of the abnormal laboratory finding and will be referred for follow-up with his/her primary care physician or other appropriate medical care. Lab results may be sent to participant's primary care physician or other treatment providers. Copies of lab-work will be made available to participants upon their request. Clinically significant abnormal laboratory findings may be repeated to determine the participant's eligibility for the study.

In the case of serious medical illness and/or abnormal laboratory findings that emerge in the course of the study, the study physician may determine that a participant should be terminated or excluded from the study.

Pharmacy Oversight

The study compound will be kept in a locked freezer which is monitored daily for temperature by a computerized monitoring system. Supplement storage and audits will be performed quarterly by the Sheppard Pratt study pharmacist, [name].

Minimizing Risk

Participants will be maintained on their regular psychotropic medications, with the intent to avoid any changes in dose or medication. Each participant will be instructed and expected to

continue treatment with his/her mental health providers and to remain on his/her prescribed psychotropic medications throughout the study. During the study, participants will be seen on a bi-weekly basis during scheduled visits and assessed for the presence of any adverse events.

If a participant reports psychiatric symptoms that raise concern about safety such as imminent, potentially-dangerous behavior, research staff will consult with the principal investigator and/or study physician and may contact the participant's current treatment providers. Permission to contact treatment providers will be obtained at the screening visit and updated as necessary throughout the study if providers change. Research staff will encourage participants to seek immediate help in these cases. Additionally, research staff may arrange for emergency assessment if a participant presents as a danger to self or others, in consultation with the principal investigator and/or the study physician. If safety cannot be assured, research staff will call 9-1-1.

Privacy and Confidentiality

Confidentiality will be protected by ensuring all research staff have been properly trained in confidentiality and human participant research procedures, coding all participant information when possible, and by securing participant files in locked filing cabinets or on secured databases with access available only to the research staff. Furthermore, data entered into a computer database will be stored on secured computers that will be password-protected with access available only to the research staff. Any screening information obtained from potential research participants who subsequently do not participate in the research study will be destroyed.

Data obtained in this study will be shared with the National Database for Clinical Research Related to Mental Illness (NDCT), which is required by the funding source. NDCT is a data repository run by the National Institute of Mental Health (NIMH) that allows researchers to collect and share de-identified data from studies related to mental illness. Other researchers may apply to obtain access to de-identified data from this study. The NIMH carefully analyzes each request in order to minimize risks of privacy. The information provided to NDCT may help researchers around the world treat future children and adults with mental illnesses so that they have better health outcomes. Participants will not be contacted directly about the study data shared during and after their research participation, and no protected health information will be entered into the NDCT.

Adverse Effects and Drug Interactions

Broccoli sprouts have been widely marketed throughout the world as a food source. Oral broccoli sprout preparations have been used in a number of human studies as described above to investigate the pharmacologic properties, safety, and biological effects of sulforaphane glucosinolates. Avmacol® supplements have been available to the public since 2013. The manufacturer reports that as of February 15, 2016, over 12,000 bottles have been distributed and there have been no reported adverse events from consumers in the general public.

Potential adverse effects that might be expected include mild GI symptoms such as indigestion, belching, or loose stools. These are the only symptoms that have been reported in the many clinical trials of glucoraphanin-rich or sulforaphane-rich broccoli sprout extracts (Alumkal et al. 2015; Cornblatt et al. 2007; Egner et al. 2011; Egner et al. 2014; Fahey, Talalay, & Kensler

2012; Heber et al. 2014; Kensler et al. 2012; Poulton et al. 2013; Riedl, Saxon, & Diaz-Sanchez 2009; Shapiro et al. 2006; Shapiro, Fahey, Wade, Stephenson, & Talalay 1998; Shapiro, Fahey, Wade, Stephenson, & Talalay 2001; Singh et al. 2014; Ye et al. 2002). True allergic reactions to broccoli (as opposed to intolerance or taste aversion) have never been reported. Sulforaphane might decrease how quickly the liver breaks down some medications because of the modulation of cytochrome enzymes such as P450; however, the extent of this effect is expected to be limited at the doses we are using. Moreover, the effects of sulforaphane on the modulation of drug metabolism/transport enzymes are varied and may serve to increase or to decrease the blood levels of medications that are metabolized by the liver (Fimognari, Lenzi, & Hrelia 2008). We will measure blood levels of antipsychotic medications at the beginning and end of the trial with tests performed by a local clinical laboratory.

It is of note that numerous other factors influence drug interactions in addition to P450 isoenzymes including age, gender, smoking, and genetic factors. Also, 30 to 40% of the participants in the previous Singh et al. (2014) study in adult autism were receiving antipsychotic medications; per the principal investigator of this study, clinical worsening was observed in only one subject and he turned out to be on placebo ([name], personal communication, Sept 4, 2015).

Adverse Events and Reporting

For the purposes of collecting and evaluating all information found during this trial, an adverse event is any undesirable or unexpected experience that occurs after informed consent has been obtained without regard to the possibility of a causal relationship, and without regard to treatment group assignment. A serious adverse event is any adverse event that: results in death; is life threatening; results in inpatient hospitalization or prolongation of existing hospitalization; results in a persistent or significant disability/incapacity; or results in congenital anomaly/birth defect. For all adverse events, research staff will question the participant regarding the occurrence and nature of the event and will document the information obtained. Adverse events shall be followed until they return to baseline or stabilize regardless of whether the participant has discontinued the study early or completed the final study visit, visit 11 (week 18); if occurring at the end of the study, the adverse events will be referred to the participant's primary care physician and/or other treatment provider for continued treatment and/or follow-up. All serious adverse events will be documented and reported to the Institutional Review Board (IRB) within the required time period. All adverse events will be summarized in a report at intervals requested by the IRB and the overseeing Data Safety Monitoring Board.

7. STATISTICAL ANALYSIS

Power calculations indicate that a sample size of N=64 has 80% power to find an effect size of d = .76 with an alpha = .05 and a two-tailed test of change between groups from screening to end of study.

Aim 1: Safety data will be analyzed using incidence density analysis, to compare rates of adverse events across groups, as well as survival analysis, to assess group differences in retention. PANSS total scores will be the primary efficacy endpoint. Repeated-measures regression models will be used to assess the main effects of group and time, plus the time by group interaction. This method is able to utilize all available data from participants with

incomplete follow-up, thus including participants who drop out of the study. (Based on our experience in previous trials with this population, we anticipate attrition of about 15% over the course of the trial.) A similar analytical approach will be used for the PANSS subscales and the MCCB outcome measures.

Aim 2: Repeated measures regression modeling will also be used to evaluate the effect of medication group, time, and their interaction on inflammatory biomarkers.

Aim 3: Treatment groups will be compared with respect to initial and follow-up levels of inflammatory biomarkers using *t*-tests. If groups are found to differ in this regard, the efficacy analyses will be repeated, adding the initial biomarker levels as covariates in the model.

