1. INTRODUCTION AND OVERVIEW

We intend to explore the hypothesis that symptoms of schizophrenia may be reduced by the administration of a sulforaphane compound when used in addition to standard antipsychotic medications. Sulforaphane is a molecule that belongs to the isothiocyanate group of organosulfur compounds found in broccoli sprouts. Sulforaphane has potent anti-oxidant and anti-inflammatory activities (Juge, Mithen, & Traka 2007). A recent trial in adolescent and young adult males with autism spectrum disorder found that sulforaphane treatment as an add-on medication was associated with improved psychiatric symptoms (Singh et al. 2014). To date, there have not been any controlled studies of sulforaphane in persons with schizophrenia. The proposed trial is justified on the grounds that: 1) oxidative stress is associated with the pathophysiology of schizophrenia and sulforaphane has anti-oxidant and anti-inflammatory properties; 2) positive effects of sulforaphane have been found in autism, a disorder with some similarities to schizophrenia; and 3) the compound has relatively low toxicity and a low side effect profile. If this sulforaphane compound is found to be beneficial, it would provide a safe, inexpensive, and widely-available new modality for the adjunctive treatment of schizophrenia.

We will randomize N=64 participants with schizophrenia or schizoaffective disorder who have residual psychotic symptoms which are of at least moderate severity. The participants will receive the sulforaphane compound 6 tablets once per day (equivalent to ~ 100 micromoles (µmol) of sulforaphane) or placebo 6 tablets once per day, over the 18 weeks of the trial. We have selected the 18 week duration of the trial to maximize both the likelihood of obtaining a therapeutic effect and of retaining participants in the study. This is also similar to the duration of the active phase in the published autism trial (Singh et al. 2014).

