5. STUDY DESIGN AND PROCEDURES

Study Overview

Over a two year period, we will randomize N=64 participants who have residual psychotic symptoms which are of at least moderate severity. Based on our experience performing similar clinical trials, we anticipate that we will evaluate up to 100 participants in order to randomize 64. We expect a drop-out rate of 15% after randomization. The trial will begin with a 2 week singleblind placebo run-in phase followed by a 16 week double-blind phase. During the placebo run-in phase, participants will receive placebo 6 tablets once per day. During the double-blind phase, participants will receive either the sulforaphane tablet 6 tablets once per day (equivalent to ~100 umol of sulforaphane) or the placebo 6 tablets once per day. The primary outcome that will be assessed is the severity of psychiatric symptoms as measured by the Positive and Negative Syndrome Scale (PANSS) (Kay et al. 1987). We will also measure cognitive functioning with the MATRICS Consensus Cognitive Battery (MCCB) (Nuechterlein et al. 2008). In addition, we will study the effect of the sulforaphane compound in lowering several biomarkers of inflammation including C-Reactive Protein (CRP), heat shock protein 90, and other markers of inflammation and cell damage. We will also investigate the association between the efficacy of sulforaphane therapy and initial and follow-up levels of these markers. For a detailed list of procedures and assessments at each study visit, see the Schedule of Assessments.

Study Compound

The active study compound and identical-appearing placebo will be prepared and provided by Nutramax Laboratories, Edgewood, MD, USA, the company that makes Avmacol®, a commercially-available over-the-counter compound (http://www.nutramaxstore.com/avmacolreg-60-tablets-p430.aspx). The active ingredient in Avmacol® is produced naturally by extracting the biologically inactive glucosinolate, glucoraphanin, from broccoli seeds, and compressing it in tablets with active myrosinase from broccoli sprouts. The ingestion of this compound leads to the

hydrolysis of glucoraphanin and the generation of sulforaphane within the gastrointestinal (GI) tract and the subsequent systemic absorption of the sulforaphane.

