These blood, throat swab, and urine samples will be identified by participant number only when they are sent to the research laboratories at Johns Hopkins for analysis. The clinical investigators will be blind to these results of the participant's research laboratory tests during the course of the trial. The laboratory scientists will be blind to the participant's treatment assignment during the course of the trial.

Placebo Lead-In Phase

Participants will begin a 2 week single-blind placebo phase at visit 2 (week 0), within 7 to 30 days of completion of the screening visit. Visit 2 (week 0) will take approximately two to three hours to complete. Participants who complete the two week placebo run-in phase and continue to meet eligibility criteria will be randomized to a treatment arm at visit 3 (week 2).

Randomization and Double-Blind Treatment Phase

Double-blind randomization will occur at visit 3 (week 2). Participants will be randomized to receive either the sulforaphane compound or placebo tablets which are indistinguishable from the sulforaphane tablets for the 16 weeks of the double-blind phase. Symptom evaluations will be completed at bi-weekly study visits at which time participants will also be evaluated for adverse events. Visits 3 to 10 (weeks 2 to 16) will take approximately one hour each to complete. Visit 11 (week 18) will take approximately two to three hours to complete.

Randomization will assure that out of N=64 total participants, approximately half are assigned to each treatment arm. In addition, block randomization, based on initial PANSS total scores, will be used to assign participants to the two treatment groups to avoid differences in initial PANSS scores between the groups. Only the study data manager and the study pharmacist will be aware of participant assignment during the trial.

Treatment providers will be asked to maintain participants on the same psychotropic medication regime throughout the study. At each bi-weekly study visit, research staff will document any medication changes. Any medication changes that are made will be studied as a secondary outcome.

The study compound will be taken once per day and the dose will not be adjusted throughout the trial.

Visit Windows

Visit 2 (week 0) will take place 7 to 30 days after visit 1 (screening). Visits 3 to 11 (weeks 2 to 18) will take place 12 to 16 days after the previous visit. Visits may be divided into separate sessions to minimize participant fatigue.

Compliance

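### Does the stated 80% power for d = .76 with 64 participants fail to reproduce?

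*Combined protocol and SAP*

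**What the plan says.** Section 7 (Statistical Analysis) gives the only sample-size justification: "a sample size of N=64 has 80% power to find an effect size of d = .76 with an alpha = .05". The same sentence fixes the error rate, the sidedness and the comparison: "alpha = .05 and a two-tailed test of change between groups from screening to end of study". It names no formula or software, and it does not say whether the figure refers to everyone randomized or to those remaining at the end.

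The other inputs stand elsewhere. Section 1 sets the size: "We will randomize N=64 participants with schizophrenia or schizoaffective disorder". Section 5 (Randomization and Double-Blind Treatment Phase) sets the allocation: "out of N=64 total participants, approximately half are assigned to each treatment arm". Expected losses appear twice, in the Study Overview of Section 5, "We expect a drop-out rate of 15% after randomization", and under Aim 1 in Section 7, "we anticipate attrition of about 15% over the course of the trial". The primary efficacy analysis is a repeated-measures regression, chosen because it keeps participants whose follow-up is incomplete: "This method is able to utilize all available data from participants with" partial follow-up.

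**The concern.** The natural first check is a two-sample t-test with 32 per arm. It misses the stated figure by about 5 points of power, or about .05 in d. The natural second check removes 15% of the participants and repeats the exact t calculation. It misses on the other side, with d of about .78 instead of .76. With one result on each side of the stated value and neither equal to it, an arithmetic error seems likely.

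If it were one, it would matter. This is the only statement of what the trial can detect, and a null result would be read against it. A figure that was too favourable for the participants expected to finish would make such a result look more conclusive than it is.

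**Working it through.** **Inputs.** N = 64 (Sections 1 and 7); about 1:1 allocation, so 32 per arm (Section 5); two-sided α = .05 and 80% power (Section 7); attrition of about 15% (Sections 5 and 7).

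**Formulas (normal approximation, n per arm).**

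- Detectable effect: d = (z₀.₉₇₅ + z₀.₈₀) × √(2/n), with 1.9600 + 0.8416 = 2.8016.
- Power = Φ(d × √(n/2) − 1.9600).

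**1. The plan's figure, with its attrition applied.** 64 × 0.85 = 54.4, so n = 27.2.

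- d = 2.8016 × √(2/27.2) = 2.8016 × 0.2712 = .7597, which rounds to .76.
- Power at d = .76: .76 × √13.6 = 2.803; 2.803 − 1.960 = 0.843; Φ(0.843) = 80.0%.

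Both halves of the stated pair, 80% and .76, come out.

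**2. The same calculation backwards.** For d = .76, n = 2 × (2.8016/.76)² = 27.18 per arm, or 54.36 in total. Dividing by 0.85 gives 63.95, so 64 to be randomized. Rounding up to 28 per arm before allowing for losses gives 56/0.85 = 65.9, so 66, which is within two participants of the plan.

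**3. All 64, without attrition.** d = 2.8016 × √(2/32) = .700, and power at .76 is Φ(3.04 − 1.96) = 86.0%. The exact noncentral t gives .711 and 84.9%. The stated figure is not reproduced on this basis by either method.

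**4. Both methods side by side.**

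| Participants analysed | d at 80%, normal | d at 80%, exact t | Power at .76, normal | Power at .76, exact t |
|---|---|---|---|---|
| 64 (32/32) | .700 | .711 | 86.0% | 84.9% |
| 56 (28/28) | .749 | .762 | 81.2% | 79.8% |
| 55 (27/28) | .756 | .770 | 80.5% | 79.0% |
| 54.4 (27.2 per arm) | .760 | .774 | 80.0% | 78.6% |
| 54 (27/27) | .763 | .777 | 79.7% | 78.2% |

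At 54.4 participants the whole difference between .760 and .774 comes from the choice between the normal and the t distribution. In power it is 80.0 − 78.6 = 1.4 points. With 27 whole participants per arm, the exact t falls 80 − 78.2 = 1.8 points short of the stated value. Section 7 commits to neither method, so a figure from the normal approximation cannot be called an error because the exact t differs in the second decimal.

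The attrition figure is itself approximate. Even by exact t, 56 participants give .762 and 79.8%; that corresponds to a loss of 8/64 = 12.5%, close to the stated rate.

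**The case for a change.** The strongest counter-argument is textual. The sentence attaches 80% and .76 to N = 64, and for 64 analysed participants neither method gives that pair. Agreement needs two things the sentence does not state: an allowance for losses and a large-sample formula. The 15% under Aim 1 appears in a remark about the regression model, not in the power statement. There is also a rival explanation: by exact t, all 64 participants give 85% power at d = .761, so the 80% could be a misprint for 85%.

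Part of this stands. The documents do not say that the figure is net of attrition, and the match does not prove how the number was obtained. What does not follow is that the figure is irreproducible. One standard formula and the plan's own attrition rate return it to two decimals, with no misprint needed. Under the rival explanation, or on a literal reading, the stated 80% is lower than the true value, so the trial promises less than it would deliver.

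The worry that the figure is optimistic for completers has little force either. By exact t the shortfall is under 2 points, and .76 and .78 support practically the same reading of a null result. The primary model is also not a t-test on 54 completers: the PANSS is scheduled at every visit, and participants who leave early still contribute data. The two-sample exact t figures for 54 and 64 participants, 78.2% and 84.9%, lie on either side of the stated 80%.

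A power figure for a baseline-adjusted contrast at week 18 would be closer to the planned analysis. It needs a correlation that the documents do not give, so its absence is no error in the figure that is there.

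**Conclusion.** The concern does not hold. The stated power follows from the plan's own inputs: 64 randomized, 15% lost, equal arms, two-sided α = .05 and the normal approximation give d = .7597 and 80.0% power. The exact t on the same basis gives 78.2% to 78.6%, a difference of method amounting to less than 2 points. Read for all 64, the sentence is conservative, with true power of about 85%.

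This rests on two assumptions that the documents do not confirm: that the calculation allowed for attrition, and that it used the normal approximation. If either is wrong, the figure is still within 2 points of the exact value for the expected completers, or about 5 points too low for the full sample. What remains is an omitted explanation. Supplying it would alter no enrolment target, analysis or conclusion.

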Pill counts and/or participant reports of compliance will be obtained. If pill counts or participant reports indicate the participant has not taken all of the prescribed study compound, the participant will be counseled about the importance of following directions. If the participant has missed more than 32 daily doses cumulatively throughout the study (>25% of study drug), the participant will be terminated from the study.

Compliance will also be confirmed with laboratory testing of urine samples provided by participants at 3 points during the trial (visits 2, 7, and 11). Participants will be told that these samples will be collected at random. These urine samples will be used to measure sulforaphane-glutathione metabolites in [name] laboratory.

Discontinuation

A participant may be discontinued from the study for any of the following reasons:

- If the participant fails to follow study directions (failure to keep appointments, follow directions or take the study compound as instructed)
- If the participant does not attend study visits, or is not in contact with research staff for 3 bi-weekly consecutive study visits
- If the participant has a positive drug screen, research staff will inform the participant that a repeat test will be done at the next visit; if the next test is positive then she/he will be removed from the study
- If it is the judgment of the study physician, in an effort to improve the participant's medical care, or if the participant develops a serious medical illness, becomes pregnant, or begins breast feeding
- If the participant has unexpected or serious side effects or serious medical complications

If a participant discontinues from the study, discontinuation assessments will be done at the discretion of the principal investigator.

A participant may withdraw from the study at any time at his/her own request.

Clinical Outcome Measures

• The primary outcome measurement will be the change in scores on the Positive and Negative Syndrome Scale (PANSS) (Kay et al. 1987) from the beginning to the end of the double-blind treatment phase, visits 3 to 11 (weeks 2 to 18). The PANSS contains 30 items that assess symptoms of schizophrenia including positive, negative and general symptom psychopathology. The PANSS was chosen because of its widespread use in clinical studies of psychosis and its demonstrated reliability in assessing psychopathology across diverse patient populations.

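### Does the adverse-event rate comparison in Section 7 need written rules for person-time, repeat events and variance?

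*Combined protocol and SAP*

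**What the plan says.** Section 7 (Statistical Analysis, Aim 1) states: "Safety data will be analyzed using incidence density analysis, to compare rates of adverse events across groups". Retention is compared separately by survival analysis. No person-time rule, counting rule, test or variance is given for the event rates.

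The related text is elsewhere in the same document:

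- **Collection.** Section 5 (Randomization and Double-Blind Treatment Phase): "Symptom evaluations will be completed at bi-weekly study visits at which time participants will also be evaluated for adverse events". The schedule in Section 9 marks adverse-event checks from visit 2 to visit 11.
- **Spacing.** Section 5 (Visit Windows): "Visits 3 to 11 (weeks 2 to 18) will take place 12 to 16 days after the previous visit".
- **Leaving early.** Under Section 5 (Discontinuation), a participant who "is not in contact with research staff for 3 bi-weekly consecutive study visits" may be discontinued, and "discontinuation assessments will be done at the discretion of the principal investigator". Section 7 adds that "we anticipate attrition of about 15% over the course of the trial".
- **Follow-up of events.** Section 6 (Adverse Events and Reporting): "Adverse events shall be followed until they return to baseline or stabilize regardless of whether the participant has discontinued the study early". The same section defines an adverse event as one occurring after informed consent.

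**The concern.** An incidence density is a count divided by time at risk, and Section 7 defines neither part. Several readings seem open:

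- The clock might start at consent, at the run-in or at randomisation.
- It might stop at the last adverse-event check or at the discontinuation date, which can fall three missed visits later.
- A complaint present at every check from visit 4 to visit 11 might be one event or eight records.
- With no variance named, a plain Poisson interval could be used. It is too narrow when people differ in their underlying event rates.

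Safety stands beside efficacy in the primary aim, and this is the only named between-arm comparison of adverse events. Choices left unwritten could be made after the data are seen, and a reader could not tell from the plan which rate had been compared.

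**Working it through.** The plan gives no figure for this analysis, so there is none to reproduce. Inputs from the documents: 64 participants, about 32 per arm; 16 weeks (112 days) double-blind; 15% attrition; checks 14 days apart (12 to 16). Assumptions, because the documents are silent: a true rate ratio of 2.0, 1 to 2 events per person, and between-person dispersion k = 0.5.

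**Start and persisting complaints.** Section 7 compares rates across groups, and Section 5 forms the groups at visit 3. Events before that belong to no arm. The consent-based definition in Section 6 governs what is collected, not time at risk. Section 6 also follows an event until it returns to baseline or stabilises, which makes a continuing complaint one event with follow-up. Incidence counts new onsets, so eight sightings of one unresolved complaint are not eight events.

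**End of person-time.**

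- Three missed visits: 3 × 14 = 42 days (36 to 48).
- Drop-outs: 0.15 × 64 = 9.6, about 10.
- Unfavourable case: all 10 are lost silently after a last check at day 56, and the clock runs to discontinuation. Unassessed time is 10 × 42 = 420 days, and its share is 420 / (54 × 112 + 10 × 56 + 420) = 420 / 7,028 = 6.0%.
- Each arm's rate is multiplied by observed days / (observed + unassessed days):

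| Drop-outs, active/placebo | Active factor | Placebo factor | Ratio (true 2.0) |
|---|---|---|---|
| 5/5 | equal | equal | 2.00 |
| 6/4 | 3,248/3,500 = 0.928 | 3,360/3,528 = 0.952 | 1.95 |
| 8/2 | 3,136/3,472 = 0.903 | 3,472/3,556 = 0.976 | 1.85 |

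Reversing the splits gives 2.05 and 2.16. If drop-out is unrelated to arm, a split within 4 to 6 per arm has probability 672/1,024 = 66%. A split of 8/2 or more extreme in either direction has 112/1,024 = 11%.

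These shifts can be set against sampling error. The standard error of the log ratio is √{[(1/μ₀ + k) + (1/μ₁ + k)] / 32}, with μ₀ and μ₁ the mean events per person on placebo and active.

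- μ₀ = 1, μ₁ = 2: √(2.5/32) = 0.280, 95% interval 1.16 to 3.46.
- μ₀ = 2, μ₁ = 4: √(1.75/32) = 0.234, 95% interval 1.26 to 3.16.

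A move to 1.95 is ln(2/1.95) = 0.025, about 0.1 standard error. A move to 1.85 is 0.078, about 0.3.

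**Variance.** The true error rate of a nominal 5% plain Poisson test is 2 × [1 − Φ(1.96 / √(1 + kμ))]. With k = 0.5:

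| Events per person, μ | Error rate |
|---|---|
| 0.2 | 6% |
| 0.5 | 8% |
| 1 | 11% |
| 2 | 17% |

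With k = 0 it is 5%. Simulation with 32 per arm and 15% leaving early gave 10% and 16% at μ = 1 and 2. A per-person robust variance gave 5.6% to 7.5% for 1 to 3 events and dispersion 0 to 2. Negative binomial regression gave about 5% to 7% across the settings tried.

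**The case for a change.** The strongest case for writing the rules down is that the default of counting post-randomisation events does not settle everything. Nothing fixes the end of the clock when contact is lost and a discontinuation assessment is optional. The expected effects in Section 6 are mild gastrointestinal symptoms, which can resolve and return, so the recurrence rule has practical meaning. If events cluster within people, the variance choice could double or triple the false-positive rate. A few lines before unblinding would cost almost nothing.

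What stands is narrow: the end of person-time, recurrence or worsening, and the variance are indeed unstated. What does not stand is the step from there to a flawed analysis. The larger end-of-clock shifts need every drop-out to be a silent loss at mid-phase and a lopsided split as well. The inflated error rate belongs to a test the plan does not name, at event rates it does not give. Negative binomial regression would fill an open choice rather than replace a worse stated one, and a robust variance does about as well. More detailed wording also raises new questions, such as whether a complaint that worsens without resolving is one event or two, and how to treat an event learned of after the last check.

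**Conclusion.** No change follows. This is a gap of detail that an analyst would fill sensibly: time at risk from visit 3 to the last check at which events were asked about, new onsets counted, and an interval that allows for differences between people. The size is small where it can be judged. With a true ratio of 2.0 and all ten expected drop-outs lost silently at day 56, the less favourable stopping rule leaves the ratio between 1.95 and 2.05 for splits of 4 to 6 per arm, and between 1.85 and 2.16 at 8/2. The 95% interval would run from about 1.16 to 3.46, or 1.26 to 3.16 at the higher event rate. The 11-17% error rate applies only if a plain Poisson variance were chosen and events were as frequent and clustered as assumed.

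No stopping or success rule uses the comparison. The safety board and the summary reports in Section 6 provide separate oversight, and neither the sample size nor the PANSS analysis is affected. The conclusion would be less comfortable if the plan had named a plain Poisson test or tied a decision to its result. It does neither.
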